6.1 Safety Analysis Set

The Safety Analysis Set is defined as all subjects that are enrolled and receive at least 1 dose of AMG 510.

6.2 Pharmacokinetic Analyses Set(s)

The PK Analysis Set will contain all subjects who have received at least dose of AMG 510 and have at least 1 PK sample collected. These subjects will be evaluated for PK analysis unless the number of data points required for analysis is not enough, or significant protocol deviations have affected the data, or if key dosing or sampling information is missing.

6.3 Study-specific Analysis Sets

6.3.1 DLT Evaluable Sets

DLT Analysis Set is defined as DLT-evaluable subjects in the Safety Analysis Set. The analysis of DLT will be conducted on the DLT Analysis Set.

The DLT analysis set consists of subjects if either the subject experiences a DLT, or the subject does not experience a DLT and subject received at least 80% of the planned doses of investigational product within the 21-day DLT window.

6.3.2 Efficacy Sensitivity Analysis Sets

Efficacy Sensitivity Analysis Set will consist of subjects in Safety Analysis Set who have one or more measurable lesions at baseline as assessed by central review according to RECIST 1.1 criteria. This analysis set will be used for sensitivity analysis of efficacy endpoints based on central review assessment.

7. Planned Analyses

The following DLRT, primary, and final analyses of the study are planned.

7.1 Interim Analysis and Early Stopping Guidelines

7.1.1 Cohort 1 (Dose Exploration – first 6 DLT- evaluable subjects in cohort)

Safety data will be reviewed on an ongoing basis. The first DLRM will occur after the first 6 DLT-evaluable subjects enrolled in cohort 1 have the opportunity to receive 21 days treatment. In dose- level review meetings, Amgen, in consultation with the site investigators, will review all available cumulative data by cohort prior to making dose determination recommendations. Adverse events and DLTs observed in all subjects will be evaluated continuously and fully integrated into all dose level review meetings and considered in all enrollment and dosing recommendation. Additional details are provided in Protocol Appendix 3.

Protocol Number: 20190147

Date: 17FEB2022 Page 15 of 28

The DLRT will be composed of the investigations, Amgen Medical Monitor, Amgen Global Safety Officer (GSO), Amgen Early Clinical Development Manager, and Biostatistics representative. Additional members may be added as needed (eg, PK Scientist). A quorum, defined as the majority of actively screening and enrolling investigators or their qualified designee (ie, sub-investigator possessing hard copy documentation [eg, email] of the investigator's recommendation regarding the dose level review), must be in attendance for DLRM to proceed. The DLRM will be rescheduled if a quorum is not reached. Voting members of the DLRM will include the Amgen Medical Monitor, the Amgen GSO, and all actively screening and enrolling investigators or their qualified sub-investigator designee.

The Amgen Medical Monitor and GSO and the majority of actively screening and enrolling investigators participating in the DLRM must cast a positive vote indicating an acceptable safety profile was observed for AMG 510 to allow the dose level modification and/or cohort continuation/expansion to proceed. Available study data including demographics, smoking status (prior and current), medical history, concomitant medications, AEs, ECGs, vital signs, laboratory results, emerging PK or pharmacodynamics, and emerging efficacy data will be reviewed.

The following recommendations will be made by the DLRT:

- dose de-escalation recommendations
- number of subjects per cohort
- continuation, delay or termination of dosing
- change of the dosing schedule
- termination of the study

7.1.2 Cohort 2 (Dose Exploration – first 6 DLT-evaluable subjects in cohort)

If in cohort 1, DLRT makes the recommendation to open cohort 2 (720 mg), the second dose level review meeting will occur after the sixth subject enrolled in cohort 2 has had the opportunity to receive 21 days of treatment.

The same DLRT will be responsible for reviewing all cumulative available data by cohort. The same procedure and principal described in cohort 1 dose level review meeting will be applied in cohort 2 as well.

Protocol Number: 20190147

Date: 17FEB2022 Page 16 of 28

7.2 Primary Analysis

The primary analysis will occur after all subjects (6 to 12 subjects) enrolled in cohort 1 and after all 6 to 12 subjects enrolled in cohort 2 (if \geq 2 DLTs are observed in the first 6 subjects in cohort 1) have had the opportunity to complete 6 months on study or have been withdrawn from study.

7.3 Final Analysis

A final analysis is planned after all cohorts have ended the study. Primary and final analyses may be combined in case all subjects have ended study close to the time point of the primary analysis.

8. Data Screening and Acceptance

8.1 General Principles

The objective of the data screening is to assess the quantity, quality, and statistical characteristics of the data relative to the requirements of the planned analyses.

8.2 Data Handling and Electronic Transfer of Data

The Amgen Global Study Operations-Data Management (GSO-DM) department will provide all data to be used in the planned analyses. This study will use the RAVE database. The database will be subject to edit checks outlined in the Clinical Data Management Plan (DMP).

8.3 Handling of Missing and Incomplete Data

Descriptive statistics will be used to identify the extent of missing data. Missing or incomplete dates that are critical for the analysis (eg, date of death, adverse event start date) will be imputed. Details are described in Appendix B. Partial or missing death dates will be imputed prior to derivation of any endpoint that utilizes the date of death.

8.4 Detection of Bias

Lack of protocol compliance and the potential for biased statistical analyses will be examined by assessing the incidence of important protocol deviation. The clinical study team will identify and document the criteria for important protocol deviation.

8.5 Outliers

PK concentration data will be evaluated for outliners by visual inspection, and decisions to re-assay individual samples will be made in accordance with standard PK evaluation practice.

Protocol Number: 20190147

Date: 17FEB2022 Page 17 of 28

8.6 Distributional Characteristics

Where appropriate, the assumptions underlying the proposed statistical methodologies will be assessed. If required data transformations of analyses will be utilized.

8.7 Validation of Statistical Analyses

Programs will be developed and maintained, and output will be verified in accordance with current risk-based quality control procedures.

Tables, figures, and listings will be produced with validated standard macro programs where standard macros can produce the specified outputs.

The production environment for statistical analyses consists of Amgen-supported versions of statistical analysis software; for example, the Statistical Analysis System version 9.4 or later.

9. Statistical Methods of Analysis

9.1 General Considerations

Descriptive statistics will be provided for selected demographic, safety, PK and preliminary efficacy data by dose, and time as appropriate. Descriptive statistics on continues data will include means, medians, standard deviations and ranges, while categorical data will be summarized using frequency counts and percentages.

For time-to-event variables, the Kaplan-Meier (K-M) estimates and corresponding two-sided 95% confidence intervals for the median and quartiles will be provided. Graphical summaries of the data may also be presented. The K-M plot may also be provided. Subject listings for time-to-event endpoints may be provided instead of K-M estimates or Clopper Pearson exact confidence interval if the analysis set has fewer than 10 subjects.

9.2 Subject Accountability

The number and percent of subjects who were enrolled, received investigational product, discontinued from investigational product (including reasons for discontinuing, completed study, discontinued the study (including reasons for discontinuing) will be summarized. Key study dates for the first subject enrolled, last subject enrolled, and last subject's end of study will presented.

9.3 Important Protocol Deviations

Important Protocol Deviations (IPDs) categories are defined by the study team before the first subject's initial visit and updated during the IPD reviews throughout the study prior to database lock. These definitions of IPD categories, subcategory codes, and

Protocol Number: 20190147

Date: 17FEB2022 Page 18 of 28

descriptions will be used during the study. The final IPD list is used to produce the Summary of IPDs table and the List of Subjects with IPDs. In addition, a separate listing of all inclusion and exclusion deviations will be provided.

9.4 Demographic and Baseline Characteristics

The following demographic and baseline characteristics will be summarized using descriptive statistics:

- sex: (male vs. female)
- age group: (≤ 65,66-74, ≥ 75)
- age in years
- race
- height (centimeters)
- weight (kilograms)
- ECOG Performance Status (0,1,2)
- time from initial diagnosis to first dose of IP (months)
- histopathology (squamous, non-squamous)
- TNM stages (stage 0, I, II, III, IV)
- type of prior anticancer therapy
- prior lines of anti-therapy (1, 2, 3, >3)
- best response on last prior therapy
- prior radiotherapy for current malignancy (yes, no)
- prior surgery for current malignancy (yes, no)
- presence of brain metastases (yes, no)
- presence of liver metastases (yes, no)
- co-mutation of interest (if available from local testing)
- smoking history (never, former, current)

9.5 Efficacy Analyses

Table 9-1. Efficacy Endpoint Summary Table

Endpoint	Primary Summary and Analysis Method (Specify Analysis Set if Safety Analysis Set is Not Used)	Sensitivity Analysis (Efficacy Sensitivity Analysis Set)
Objective Response (OR)	The proportion of subjects with an OR will be summarized along with a Clopper-Pearson exact confidence interval. Subjects without a post-baseline tumor assessment will be considered non-responders. Use local investigator review assessment per RECIST 1.1 criteria	Use central review assessment per RECIST 1.1 criteria

Protocol Number: 20190147

Date: 17FEB2022 Page 19 of 28

Endpoint	Primary Summary and Analysis Method (Specify Analysis Set if Safety Analysis Set is Not Used)	Sensitivity Analysis (Efficacy Sensitivity Analysis Set)
Disease Control	DCR will be summarized along with a Clopper- Pearson exact confidence interval. Subjects without a post-baseline tumor assessment will be considered non-responders. Use local investigator review assessment per RECIST 1.1 criteria	Use central review assessment per RECIST 1.1 criteria
DOR	DOR will be summarized with Kaplan-Meier quartiles and rates at selected time points (eg, > 3, > 6, > 9, > 12 months). Use local investigator review assessment per RECIST 1.1 criteria	Use central review assessment per RECIST 1.1 criteria
TTR	TTR will be summarized by the non-missing sample size (n), mean, standard deviation, median, minimum and maximum for responders. Use local investigator review assessment per RECIST 1.1 criteria	Use central review assessment per RECIST 1.1 criteria
PFS	PFS will be summarized with Kaplan-Meier quartiles and rates at selected time points (eg, > 3, > 6, > 9, > 12 months). Use local investigator review assessment per RECIST 1.1 criteria	Use central review assessment per RECIST 1.1 criteria
DoSD	DoSD will be summarized with Kaplan-Meier quartiles and rates at selected time points (eg, > 3, > 6, > 9, > 12 months). Use local investigator review assessment per RECIST 1.1 criteria	Use central review assessment per RECIST 1.1 criteria

Subject listings for time-to-event endpoints may be provided instead of K-M estimates or Clopper Pearson exact confidence interval if the analysis set has fewer than 10 subjects.

9.5.1 Analyses of Primary Efficacy Endpoint(s)

There is no primary efficacy endpoint.

9.5.2 Analyses of Secondary Efficacy Endpoint(s)

All efficacy endpoints are assessed by both local investigator review and central vendor review according to RECIST 1.1 criteria. All primary efficacy analyses are conducted with local investigator assessments based on Safety Analysis Set. The efficacy endpoints assessed by central review are summarized as sensitivity analysis, based on Efficacy Sensitivity Analysis Set.

Objective response rate (ORR)

The number and proportion of subjects with an objective response (OR), defined as CR+PR (assessed per RECIST version 1.1) will be summarized along with a

Protocol Number: 20190147

Date: 17FEB2022 Page 20 of 28

Clopper-Pearson exact 95% CI. Subject without a post-baseline tumor assessment will be considered as non-responders.

Duration of response (DOR)

DOR will be calculated only for subjects who achieve a best overall response of **confirmed** PR or CR Subjects will be censored following the censoring strategy described in the definition of PFS time in Table 5-1. The distribution of DOR, including the median and quartiles will be characterized using the Kaplan-Meier (K-M) method. The 95% CI for the median and quartiles of PFS will be constructed using the method of Klein and Moeschberger (1997) with log-long transformation.

Disease control rate (DCR)

Summary of disease control is measured by disease control rate (DCR),.

DCR will be summarized along with a Clopper-Pearson exact 95% confidence interval (Clopper and Pearson, 1934). Subjects without a post-baseline tumor assessment will be considered non-responders.

Duration of stable disease (DoSD)

DoSD will be calculated **only** in subjects with best overall response of SD. Subjects will be censored following the censoring strategy described in the definition of the PFS time and will be analyzed using the same method as described for DOR.

Time to response (TTR)

TTR will be summarized by the non-missing sample size (n), mean, standard deviation, median, minimum and maximum for responders, i.e., subjects who achieve best overall response of PR or CR.

Progression free survival (PFS)

The distribution of PFS, including median, with be estimated using the Kaplan-Meier method. PFS rate at the selected time points (at 3-month intervals) will be reported. The 95% CIs for the median and other quartiles of PFS will be constructed using the method Klein and Moeschberger (1997) with log-log transformation. The rates for selected durations (eg, > 3, > 6, > 9, > 12 months) will be reported and the 95% CI will be estimated using the methods by Kalbfleisch and Prentice (1980) with log-log transformation.

Listings of secondary efficacy endpoints will be produced for all subjects.

Protocol Number: 20190147

Date: 17FEB2022 Page 21 of 28

9.6 Safety Analyses

9.6.1 Analyses of Primary Safety Endpoint(s)

Table 9-2. Safety Endpoint Summary Table

Endpoint	Primary Summary and Analysis Method
Primary	Unless otherwise specified, statistical analyses on safety endpoints will be done using subjects from the safety analysis set, which includes subjects that are enrolled and received at least 1 dose of AMG 510. The statistical methods are described in Section 9.6.2 through Section 9.6.6 and Section 9.7.1.

9.6.2 Adverse Events

The Medical Dictionary for Regulatory Activities (MedDRA) version 21.0 or later will be used to code all events categorized as adverse events to a system organ class and a preferred term.

Subject incidence of all treatment-emergent adverse events, fatal adverse events, serious adverse events, adverse events leading to withdrawal of investigational product, treatment-related adverse events and adverse events of interest will be tabulated by system organ class and preferred term.

Abnormal pregnancy outcome (eg, spontaneous abortion, fetal death, stillbirth, congenital anomalies, ectopic pregnancy) are considered serious adverse events.

The severity of each adverse event will be graded using The Common Terminology Criteria for Adverse Events (CTCAE) version 5.0 criteria.

9.6.3 Laboratory Test Results

The analyses of clinical laboratory test will include summary statistics over time and/or changes from baseline over time will be provided for each scheduled post-baseline assessments. Tables of maximum shift from baseline to the worst on-study value will be provided for selected laboratory values with NCI-CTCAE grade. The parameters in Appendix C will be summarized.

Subject incidence of suspected Hy's law cases (Hy's law predicts potential for drugrelated hepatotoxicity) will be summarized. A listing of alanine aminotransferase, aspartate aminotransferase, alkaline phosphatase, and total bilirubin values at each time point will be produced for the subjects suspected of Hy's law case.

Protocol Number: 20190147

Date: 17FEB2022 Page 22 of 28

Unscheduled assessments will be included in the shift tables.

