2.3 Benefit/Risk Assessment

Based on preclinical data, nonclinical toxicity studies, and the clinical experience with AMG 510, the overall benefit/risk profile favors clinical development of AMG 510 for subjects with *KRAS p.G12C*-driven cancers.

As of 17 July 2019, 76 subjects with *KRAS p.G12C* advanced or metastatic tumors were enrolled in the study. Of these 76 subjects, 34 (44.7%) had NSCLC, 35 (46.0%) had CRC, and 7 (9.2%) had other solid tumors. Fifty-five subjects were evaluable (ie, had 6-week response data or early progression). Of the 55 enrolled subjects with all cancer types who were evaluable, 13 subjects had partial response (PR) and 34 subjects had stable disease; the response was not evaluable for 1 subject.

Based on nonclinical toxicity studies of AMG 510, the key safety information to be monitored in clinical studies includes renal toxicity, anemia, leukocytosis, **thyroid abnormalities**, and splenomegaly. Based on clinical study data, the key **risks** to be monitored includes increases of AST and ALT, **and interstitial lung disease (ILD)/pneumonitis.** Clinical signs and symptoms of the key safety information, along with safety laboratories, will be monitored during the study to ensure the subjects' safety.

The above benefit risk assessment supports the conduct of this clinical trial. Reference should be made to the Investigator's Brochure for further data on AMG 510.

COVID-19 Related Benefit/Risk Assessment

Amgen closely monitors the coronavirus disease-2019 (COVID-19) pandemic around the world. As part of this effort, Amgen performs a rigorous assessment, considering the study design, patient safety, public health risk, benefit-risk assessment, as well as the burden on country healthcare systems. Decisions are made on a study-by-study and country-by-country basis to minimize risk to patients and avoid undue burden on healthcare facilities.

Patients who display symptoms consistent with COVID-19 infections or who have tested positive for COVID-19, should contact the investigator to ensure appropriate care as well as documentation and management of study activities.

Amgen considers that it is important to continue the proposed development of AMG 510 in this study in order to advance potential therapy options for patients as rapidly as possible, while balancing this with appropriate measures to monitor and mitigate the potential impact of COVID-19.

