11.2 Appendix 2. Clinical Laboratory Tests

The tests detailed in Table 11-1 will be performed by the central laboratory and/or by the local laboratory.

Protocol-specific requirements for inclusion or exclusion of subjects are detailed in Sections 5.1 to 5.2 of the protocol.

Additional tests may be performed at any time during the study as determined necessary by the investigator or required by local regulations.

Local Laboratory: Chemistry	Local Laboratory: Coagulation	Local Laboratory: Urinalysis	Local Laboratory: Hematology	Central Laboratory
sodium potassium chloride bicarbonate total protein albumin calcium magnesium phosphorus glucose BUN or urea creatinine total creatine kinase total bilirubin direct bilirubin direct bilirubin ALP AST (SGOT) ALT (SGPT) Glomerular filtration rate (derived)	PT/INR PTT/aPTT fibrinogen (optional) D-dimer (optional) Local Laboratory: Serology Hep B surface antigen Hep C antibody Anti-HBs Local Laboratory: Thyroid Panel TSH Total T3 (or free T3 per local standard) Free T4 Local Laboratory: Lipid Panel total cholesterol LDL	specific gravity pH blood protein glucose bilirubin ketones sodium (optional) potassium (optional) Microscopic exam ^c : • cellular casts • granular casts • hemoglobin casts • hyaline casts • hyaline casts • mixed casts • WBC • RBC • epithelial cells • bacteria • urine casts	RBC hemoglobin hematocrit MCV platelets calculated absolute neutrophil count (derived) WBC differential: • total neutrophils • bosophils • basophils • lymphocytes • monocytes	PK sampling tumor biopsy ^b

Table 11-1. Analyte Listing

Local Laboratory: Chemistry	Local Laboratory: Coagulation	Local Laboratory: Urinalysis	Local Laboratory: Hematology	Central Laboratory
	HDL			
	triglycerides			
	Local Laboratory: Other			
	HbA1c			
	Serum or urine pregnancy ^a			

Footnotes defined on next page

ALP = alkaline phosphatase; ALT = alanine aminotransferase; aPTT = activated partial thromboplastin time; AST = aspartate aminotransferase; BUN = blood urea nitrogen; HbA1c = hemoglobin A1c; HDL = high density lipoprotein; Hep = hepatitis; HIV = human immunodeficiency virus; INR = international normalized ratio; LDL = low density lipoprotein; MCV = mean corpuscular volume; PK = pharmacokinetics; PT = prothrombin time; PTT = partial thromboplastin time; RBC = red blood cell count; SGOT = serum

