Appendix C. Analyte Listing

Local Laboratory						
Chemistry	Hematology	Coagulation	Lab parameter for shift tables			
Sodium	RBC	PT or INR	Albumin			
Potassium	Hemoglobin	aPTT	Alkaline Phosphatase			
Chloride	Hematocrit	Fibrinogen	Activated partial			
Bicarbonate	MCV	(optional)	thromboplastin time			
Total protein	Platelets	D-Dimer	Bilirubin			
Albumin	Calculated absolute	(optional)	Calcium Corrected			
Calcium	neutrophil count		Creatine Kinase			
Magnesium	(derived)		Creatinine			
Phosphorous	WBC		Fibrinogen			
Glucose	Differential		Glucose			
BUN or urea	Total neutrophils		Hemoglobin			
Creatinine	 Eosinophils 		Potassium			
Total creatine kinase	 Basophils 		Lymphocytes			
Total bilirubin	 Lymphocytes 		Magnesium			
Direct bilirubin	 Monocytes 		Sodium			
ALP			Neutrophils			
AST(SGOT)	Urinalysis		Platelets			
ALT(SGPT)	Specific gravity		Protein			
Glomerular filtration	pH		Aspartate			
rate (derived)	Blood		Aminotransferase			
	Protein		Alanine Aminotransferase			
TSH	Glucose		Leukocytes			
Total T3 (or free T3	Bilirubin					
per local standard)	Ketones					
Free T4	Sodium (optional)					
Total cholesterol	Potassium (optional)					
LDL						
HDL Totalesa a sida a	Microscopic exama:					
Triglycerides	Cellular casts					
	Granular casts					
	Hemoglobin casts					
	Hyaline casts					
	Mixed casts					
	WBC					
	RBC					
	Epithelial cells Bastaria					
	Bacteria					
	 Urine casts 					

ALP = alkaline phosphatase; ALT = alanine aminotransferase; aPTT = partial thromboplastin time; AST = aspartate aminotransferase; HepBsAg = hepatitis B surface antigen; HepCAb = hepatitis C antibody; HDL = high density lipoprotein; Hep = hepatitis; INR = international normalized ratio; LDL = low density lipoprotein; PT = prothrombin time; PTT = partial thromboplastin time; RBC = red blood cell count; T3 = triiodothyronine; T4 = thyroxine; TSH = thyroid stimulating hormone; WBC = white blood cell count.

Note: For creatinine clearance calculation, Modification of Diet in Renal Disease formula should be used: GFR (mL/min/1.73 m2) = 175 x SCr (mg/dL)-1.154 x age-0.203 x 0.742 (if female) x 1.21 (if African American) x 0.763 (if Japanese) x 1.233 (if Chinese).

^aMicroscopic exam to be performed at the discretion of the investigator.

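### No planned laboratory table counts subjects whose TSH, T3 or free T4 moved from normal to abnormal, although the protocol lists thyroid abnormalities as key safety information

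*SAP*

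**What the plan says.** Protocol 2.3 draws two lists. The first rests on nonclinical studies and "includes renal toxicity, anemia, leukocytosis, thyroid abnormalities, and splenomegaly". The second is separate: "Based on clinical study data, the key risks to be monitored includes increases of AST and ALT", together with ILD/pneumonitis. Protocol section 3 makes changes in clinical laboratory tests part of the primary safety endpoint.

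Protocol Table 11-1 places a thyroid panel with the local laboratories: TSH, free T4, and a T3 entry that begins "Total T3 (or free T3 per local standard". SAP Appendix C carries the same three tests.

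SAP 9.6.3 plans two kinds of laboratory table. One is summary statistics and/or change from baseline at scheduled assessments, and here "The parameters in Appendix C will be summarized", thyroid tests included. Under SAP 9.1 such statistics "will include means, medians, standard deviations and ranges". The other kind is the shift table: "Tables of maximum shift from baseline to the worst on-study value will be provided for selected laboratory values with NCI-CTCAE grade". Unscheduled results are stated to enter the shift tables. The tests concerned are in the Appendix C column headed "Lab parameter for shift tables", which contains no thyroid test.

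**The concern.** A shift table answers a question about subjects: how many were normal at baseline and abnormal at their worst on study. A visit-by-visit summary answers a question about the group. For a topic the protocol singles out for monitoring, the first question is the one a safety reader will ask.

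Thyroid values also have two abnormal directions, so rises and falls offset each other in a mean change. A repeat test drawn between visits because a value looked wrong has no stated place in the thyroid output, since unscheduled results are assigned only to the shift tables.

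At stake is a laboratory-only thyroid signal in a study of at most 18 subjects whose purpose is to characterise safety in a population not yet studied separately.

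**Working it through.** The plan gives no figure on this point, so there is none to reproduce. The check is a comparison of lists, a tracing of outputs and a small illustration.

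**1. Topics in Protocol 2.3 against the SAP Appendix C shift list**

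| Topic in 2.3 | Laboratory measure | In shift list? |
|---|---|---|
| Renal toxicity | Creatinine | Yes |
| Anemia | Hemoglobin | Yes |
| Leukocytosis | Leukocytes | Yes |
| AST and ALT increases | AST, ALT | Yes |
| Thyroid abnormalities | TSH, T3, free T4 | No |
| Splenomegaly, ILD/pneumonitis | Not a laboratory test | Not applicable |

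The shift list has 20 parameters and includes 0 of the 3 thyroid tests. Fibrinogen, an optional test, is on it.

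**2. Where a thyroid change could appear**

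- Over-time summaries (SAP 9.6.3): yes, for scheduled visits, with no count outside normal limits.
- Shift tables (SAP 9.6.3): no.
- Laboratory listings: the only one named in SAP 9.6.3 is for suspected Hy's law cases.
- Adverse event tables (SAP 9.6.2): yes, if the investigator reports an event. Protocol 8.2.5 says abnormal findings without clinical significance are in general not recorded.

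By contrast, SAP 9.6.6 gives ECGs categorised maximum values and changes, unscheduled results and a full listing.

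**3. Do mean, median, SD and range fix the count?** Assume n = 12, normal TSH of 0.4 to 4.5 and a baseline of 2.0 in every subject. All values are invented.

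- Set A: 0.2 (twice), 1.0 (three times), 4.0 (four times), 6.0 (three times). Sum = 0.4 + 3 + 16 + 18 = 37.4; mean = 37.4/12 = 3.12. Median = 4.0. Sum of squares = 0.08 + 3 + 64 + 108 = 175.08; SD = √[(175.08 − 37.4²/12)/11] = √5.32 = 2.31. Range 0.2 to 6.0. Abnormal: 2 low + 3 high = 5.
- Set B: 0.2 (four times), 3.0 (twice), 5.0 (five times), 6.0 (once). Sum = 0.8 + 6 + 25 + 6 = 37.8; mean = 37.8/12 = 3.15. Median = (3.0 + 5.0)/2 = 4.0. Sum of squares = 0.16 + 18 + 125 + 36 = 179.16; SD = √[(179.16 − 37.8²/12)/11] = √5.46 = 2.34. Range 0.2 to 6.0. Abnormal: 4 low + 6 high = 10.

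The changes from baseline are the same values less 2.0: means 1.12 and 1.15, median 2.0, the same SDs, range −1.8 to 4.0. The printed summaries would look alike, with 5/12 = 42% and 10/12 = 83% of subjects abnormal.

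**4. What those statistics do show.** One subject rising from 2 to 20 with 11 unchanged gives mean change 18/12 = 1.5, median 0, SD √[(18² − 12 × 1.5²)/11] = √27 = 5.2, range 0 to 18. Twelve rises of 1.5 give mean 1.5, median 1.5, SD 0, range 1.5 to 1.5. The means agree, but the other statistics separate the two cases.

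**The case against.** The strongest reply is that thyroid abnormality that matters clinically is already counted. Protocol Appendix 4 makes a clinically significant abnormal laboratory result an adverse event, Protocol 8.2.5 adds changes that require treatment or an adjustment of therapy, and SAP 9.6.2 tabulates subject incidence by preferred term. The dose level review also sees laboratory results. This stands. A reader might infer that the planned output cannot show thyroid abnormality at all; the documents do not support that. What lacks a count is abnormality by laboratory value, above all values judged not clinically significant.

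Second, the omission follows a stated rule: shift tables are for graded tests, and the documents do not say whether thyroid tests have a CTCAE grade. This explains the gap. It does not remove it, because a table against the normal range needs no grade.

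Third, SD and range are planned, so a single extreme scheduled value would be visible. This also stands, as step 4 of the working shows.

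Fourth, a reader might infer that thyroid is a key risk. Protocol 2.3 uses that term for AST/ALT and ILD/pneumonitis. Protocol 2.2.2.3 treats the dog thyroid findings, with others, as non-severely toxic and/or adaptive or secondary.

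Fifth, a reader might infer that total and free T3 will be pooled. The analyte entry says only which assay a site may use. The supportable statement is that no handling rule is given.

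**Conclusion.** The point holds in a limited form. Following SAP 9.6.3 and Appendix C as written yields no laboratory count of subjects whose TSH, T3 or free T4 moved from normal at baseline to abnormal on study. Thyroid is the one laboratory-measured topic in Protocol 2.3 treated this way.

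Its size is modest. The study is descriptive and tests no hypothesis, so no sample size or error rate is affected, and thyroid adverse events are still counted. The list comparison rests on the documents alone. The 5-versus-10 contrast rests on invented values and assumed TSH limits; it shows only that the planned statistics do not determine the count. Part of the Schedule of Activities is not visible in the available text, so the thyroid sampling times could not be checked; the finding does not depend on them.

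**What to change.** In SAP 9.6.3 and Appendix C, add shift tables for TSH, free T4 and T3 classified as low, normal or high against the local laboratory's reference range. Show baseline against the lowest on-study value and against the highest, include unscheduled results, and give number and percentage of subjects. If sites use different T3 assays, tabulate total and free T3 separately.

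The cost is one extra table and a few lines of SAP text, with no new test or visit. It requires local thyroid reference ranges in the database. The documents do not confirm that these are captured, so this should be checked first.
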